4.2 HYPOTHESIS

Focal Impulse and Rotor Modulation (FIRM) guided procedures will eliminate the source of clinical arrhythmias in subjects with indications for AF ablation procedures.

5 **STUDY OBJECTIVES**

The primary objective is to evaluate the safety and effectiveness of FIRM procedures in addition to conventional ablation for the treatment of persistent atrial fibrillation (AF).

The secondary objectives are: 1) to evaluate the acute success of FIRM-guided procedure in eliminating the source of arrhythmias, and 2) to evaluate quality of life outcomes.

6 **STUDY DESIGN**

The study is designed as a prospective, multicenter, randomized study to assess the safety and effectiveness of FIRM procedures followed by conventional ablation including PVI versus a standard PVI procedure for the treatment of de novo persistent atrial fibrillation.

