6.2 RANDOMIZATION

Block randomization using a web-based database system will be used to assign subjects (1:1) to the conventional AF ablation treatment without FIRM-guided diagnostic procedure, or to the FIRM-guided procedure followed by conventional AF ablation.

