10.2 STUDY PROCEDURE

The subject will be scheduled to undergo study treatment after the subject has met all inclusion and exclusion criteria, has signed the study informed consent form, and has completed the baseline assessments. Once enrolled in the study, the subject will be randomized to undergo either conventional AF treatment with ablation, or FIRM-guided procedure followed by conventional AF ablation.

A. *Pre-procedure Preparation*

Just prior to and/or during the procedure, a glycoprotein IIb/IIIa inhibitor or other platelet inhibitor may be administered if it is standard practice. The insertion of the FIRMap catheter or performing transseptal puncture, whichever comes first, will be followed immediately by an IV heparin bolus, followed by repeated heparin administration, adjusted as necessary to achieve and maintain an ACT above 300 seconds.

B. *Intra-procedure Guidelines*

During the procedure, the following actions should be taken and appropriate data collected. Table 6.

Table 6 – Intra-Procedure Guidelines

Parameter	Description
Vascular access	Under sterile technique, the right and/or left femoral veins may be cannulated via Seldinger, or percutaneous approach. Other vascular access also may be obtained based upon physician judgment.
Reference catheter placement	Reference catheters (including 64-pole FIRMap catheter(s)) may be inserted and placed within the heart to record signals as clinically required at the discretion of the physician.
Access to left atrium	Access to the left atrium should be according to the institution's standard practice.
Anticoagulation	Upon insertion of 64-pole FIRMap catheter or transseptal puncture (whichever comes first), an IV heparin bolus should be administered, followed by repeated heparin administration, adjusted as necessary to achieve and maintain an ACT above 300 sec.
Catheter placement	Catheters may be inserted and used according to the institution's standard practice.
Source arrhythmia diagnosis	After obtaining at least 1 minute of continuous electrograms from the 64-pole FIRMap catheter either simultaneously or sequentially in the right and left atria, these electrogram data will be transferred to the Topera RhythmView® system. This will then produce FIRMap displays which will be interpreted by the operator to determine which locations have focal or rotor rhythms that could be sources of the AF.

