16.2 Study Endpoints

A. Long-Term Effectiveness (Primary effectiveness endpoint)

Two endpoints will be used for long term effectiveness after the initial AF ablation procedure (only):

Single Procedure Freedom from AF/AT recurrence* at 3 months, and

Single Procedure Freedom from AF/AT recurrence* from 3-12 months after the initial AF ablation procedure.

Freedom from AF/AT recurrence is defined as no documented episodes of AF > 30 seconds with conventional non-invasive monitoring. In the case of a cardiac implanted electronic device (CIED), freedom from AF/AT recurrence is defined as no documented episodes of AF > 30 in a 48 to 72-hour window at the follow-up visits in addition to any symptomatic episodes with documented AF > 30 seconds. AT recurrence does not include episodes of CTI (cavotricuspid isthmus) dependent flutter.

The statistical hypothesis for this endpoint is operationalized as follows:

$H_0: p_E = p_C$

$H_A: p_E \neq p_C$

$\alpha =$ [REDACTED]

Where:

p_E = the proportion of "successes" in the FIRM arm

p_C = the proportion of "successes" in the conventional ablation control arm

The proportion of successes in each treatment arm shall be evaluated relative to their respective primary endpoint using both Chi-Square (Binomial, 1df) and by Kaplan-Meier survival estimation. Each evaluation will include 95% confidence intervals. Since there are multiple (dual) independent endpoints, each resulting p-value will be reported both as calculated, and the associated Hochberg corrected p-value.

B. Acute Effectiveness (Secondary effectiveness endpoint)

The acute success of FIRM-guided procedure is defined as elimination of the source of arrhythmias identified by FIRMap as indicated by;

1. No evidence of the source on FIRMap immediately post-procedure, OR
2. Reduction of electrogram amplitude to <0.2mV in region designated by FIRMap

The proportion of successes in each arm will be calculated as follows:

$$\frac{n}{N}$$

Where:

n = the total count of "successful" subjects in the arm in question

N = the total count of subjects for that arm in the ITT group

The statistical hypothesis for this endpoint is operationalized as follows:

$$H_0: p_E = p_C$$

$$H_A: p_E \neq p_C$$

$$\alpha = \text{[REDACTED]}$$

Where:

p_E = the proportion of "successes" in the FIRM arm

p_C = the proportion of "successes" in the conventional ablation control arm

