This endpoint will be evaluated using a Chi-Square test of independence, the proportions assumed to be binomial for each group.

C. Acute Safety (Primary safety endpoint)

The acute safety success of either treatment arm is defined as freedom from serious adverse events related to the procedure within ten (10) days of the index procedure. The proportion of successes in each arm will be calculated as follows:

$$\frac{n}{N}$$

Where:

n = the total count of subjects presenting freedom from serious adverse events related to the procedure within ten (10) days of the index procedure.

N = the total count of subjects in that arm in the ITT group

The statistical hypothesis for this endpoint is operationalized as follows:

$H_0: p_E = p_C$

$H_A: p_E \neq p_C$

Where:

p_E = the proportion of "successes" in the FIRM arm

p_C = the proportion of "successes" in the conventional ablation control arm

This endpoint will be evaluated using a Chi-Square test of independence, the proportions assumed to be binomial for each group.

D. Long-Term Safety (Primary safety endpoint)

Long-term safety is defined as freedom from procedure-related serious adverse events (SAEs) (including those related to repeat procedures) within one year of the initial procedure.

The statistical hypothesis for this endpoint is operationalized as follows:

$H_0: p_E = p_C$

$H_A: p_E \neq p_C$

$\alpha =$

Where:

p_E = the proportion of subjects free from serious adverse events related to the procedure (including from any repeat procedures required) within one year of the index procedure in the FIRM arm

p_C = the proportion of subjects free from serious adverse events related to the procedure (including from any repeat procedures required) within one year of the index procedure in the conventional ablation control arm

The proportion of events in each treatment arm shall be evaluated relative to their respective primary endpoint using both Chi-Square (Binomial, 1df) and by Kaplan-Meier survival estimation. Each evaluation will include 95% confidence intervals.

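### Section 16.2 B tests acute effectiveness between arms, but acute success is defined only for the FIRM-guided procedure and no control-arm assessment is specified

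*Protocol*

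**What the plan says.** Acute effectiveness is the only endpoint in Protocol Table 3 (section 7.3). Quality of life, also a secondary objective in section 5, is listed in Table 4 as an additional evaluation.

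- **Objective (section 5).** The aim is "to evaluate the acute success of FIRM-guided procedure in eliminating the source of arrhythmias". No comparison with control is mentioned.
- **Definition (section 16.2 B, also Table 3 and the synopsis).** "The acute success of FIRM-guided procedure is defined as elimination of the source of arrhythmias identified by FIRMap as indicated by" either of two criteria. The first is "No evidence of the source on FIRMap immediately post-procedure, OR" the second is a fall in electrogram amplitude below 0.2 mV in a region that FIRMap has designated.
- **Analysis (section 16.2 B).** A success proportion n/N is calculated in each arm, with "N = the total count of subjects for that arm in the ITT group". The hypotheses are H0: p_E = p_C against p_E ≠ p_C, where p_C is the proportion of successes in the conventional arm. Then: "This endpoint will be evaluated using a Chi-Square test of independence, the proportions assumed to be binomial for each group".
- **Allocation (section 6.2).** Controls receive "conventional AF ablation treatment without FIRM-guided diagnostic procedure".

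**The concern.** The endpoint asks whether a source found by FIRMap has been eliminated. A subject who is never mapped has no such source and no designated region, so neither criterion can be applied. The section 16.2 B hypothesis has the same form as those written for the two-arm endpoints, but its definition covers one arm only. The wording of section 16.2 C shows the difference: "The acute safety success of either treatment arm is defined as freedom from serious adverse events related to the procedure". Acute effectiveness has no such extension to either arm.

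At stake is whether the planned secondary analysis can be run at all and, if it can, whether its p-value means anything. A very small p-value could be read as superiority of FIRM in eliminating arrhythmia sources, when it would only restate that controls were not mapped.

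**Working it through.** The protocol gives no legible alpha, expected rate or power for this endpoint, so there is no stated figure to reproduce. The check has two parts.

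**1. Can p_C be obtained?**

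| Element | Protocol location | FIRM arm | Control arm |
|---|---|---|---|
| FIRM-guided diagnostic procedure | 6.2 | yes | no |
| Criterion 1: source absent on post-procedure FIRMap | 16.2 B | assessable | no assessment specified |
| Criterion 2: amplitude in FIRMap-designated region | 16.2 B | assessable | no designated region foreseen |
| Denominator | 16.2 B | full ITT count | full ITT count |

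No passage supplies another criterion for controls or says how an unmapped control is counted. Two readings follow.

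*Reading A: unmapped controls are not evaluable.* The control row is 0 successes and 0 failures. Its expected counts are zero and the chi-square statistic is undefined.

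*Reading B: unmapped controls are non-successes.* The full-ITT denominator allows this, though no passage states it. Then p_C = 0/N.

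**2. What does the test do under reading B?**

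Inputs: N per arm at most 350/2 = 175 (sections 6.1 and 6.2; the ITT definition in 16.1 may reduce it). Assumptions: equal arms and two-sided alpha 0.05, with 0.025 and 0.01 as a range.

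For k/N against 0/N the statistics reduce to:

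- Uncorrected chi-square = 2Nk / (2N − k)
- Yates-corrected chi-square = 2N(k − 1)² / [k(2N − k)]
- Two-sided Fisher p = 2 · C(N, k) / C(2N, k)

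With N = 175:

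- k = 4: uncorrected = 350 × 4 / 346 = 4.046, p = 0.044. Expected successes are only 2 per arm; Yates p = 0.131, Fisher p = 0.123.
- k = 5: uncorrected p = 0.024, Yates p = 0.072, Fisher p = 0.061.
- k = 6: Yates = 350 × 25 / (6 × 344) = 4.239, p = 0.0395; Fisher p = 0.0299; uncorrected p = 0.0135.

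Smallest k that rejects, the same at N = 100, 125, 150 and 175:

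| Assumed alpha | Uncorrected | Yates | Fisher |
|---|---|---|---|
| 0.05 | 4 | 6 | 6 |
| 0.025 | 5 | 7 | 7 |
| 0.01 | 7 | 9 | 8 |

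Six successes are 6/175 = 3.4%, 6/150 = 4.0% or 6/100 = 6.0% of the FIRM arm. The strictest threshold, nine, is 9/175 = 5.1% or 9/100 = 9.0%.

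If the true FIRM success rate were only 10% (an illustrative value, not from the protocol), the binomial probability of at least six successes is 0.9997 at N = 175, 0.998 at N = 150 and 0.94 at N = 100.

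**The case against.** The strongest counter-argument is that the two readings are not exhaustive. Table 6 (section 10.2 B) is not split by arm. It lets FIRMap catheters be placed at the physician's discretion, and its source-diagnosis row names no arm: "This will then produce FIRMap displays which will be interpreted by the operator to determine which locations have focal or rotor rhythms". Section 6.2 could be read as barring FIRM guidance rather than recording. Some controls might then be mapped, and p_C could exceed zero.

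This third reading is possible, but it does not rescue the test. No row sets a post-procedure source assessment in controls. Any successes would come from a subset chosen at the physician's discretion and be divided by the full ITT count. That p_C would reflect how many controls happened to be mapped as much as any treatment effect. What does stand is that Table 6 and section 6.2 need to be reconciled.

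A second objection is that scoring rules belong in the statistical analysis plan, to which the synopsis refers for details. That holds for pure scoring detail, such as how a FIRM subject with no identified source is counted. It does not cover the conflict here, because the protocol itself fixes the hypothesis, denominator and test, and they do not fit its own definition and allocation.

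Third, the figures depend on an assumed alpha, on reading B and on test variants that the protocol does not name (it specifies only a chi-square test). That is correct. They illustrate the size of the problem under one reading. The main point needs no arithmetic.

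Finally, the reach is limited. No primary effectiveness, safety or interim analysis uses this endpoint, no visible decision rule rests on it, and the FIRM-arm proportion is already planned. This limits the severity.

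**Conclusion.** The concern holds. As written, the between-arm test of acute effectiveness either cannot be computed (controls not evaluable) or rejects almost regardless of how well FIRM works (controls counted as 0/N). The second conclusion assumes equal arms of 100 to 175 and two-sided alpha between 0.01 and 0.05; across that range, 4 to 9 FIRM successes suffice, depending on alpha and test variant. Discretionary mapping of some controls would change p_C without making it interpretable. Nothing in this conclusion relies on redacted text, since the definition, denominator, hypotheses and test are all legible. The point should be corrected, but it is of modest weight because the damage is confined to one secondary p-value.

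**What to change.** In section 16.2 B, delete p_C, H0/HA and the chi-square test. Report acute success in the FIRM arm as a proportion of its ITT count with a 95% confidence interval. This answers the secondary objective as section 5 states it. A second proportion, restricted to FIRM subjects with a FIRMap-identified source, may be shown beside it.

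Reconcile the Table 6 rows on reference catheter placement and source diagnosis with section 6.2, so that it is clear whether they apply to controls.

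If the sponsor does want an acute comparison between arms, it would need a different endpoint, defined and assessed in the same way in both arms. That is a larger change.

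The recommended change to 16.2 B is wording only. It gives up a p-value without meaning and leaves the sample size and primary analyses as they are. Clarifying Table 6 is also a wording change; it would affect data collection only if FIRMap recording in controls had in fact been intended.

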4 BACKGROUND AND RATIONALE

Atrial fibrillation (AF) is the most common sustained arrhythmia in man, and has an increasing population prevalence over time. Treatment is aimed at stroke prevention on the one hand, and amelioration of symptoms (palpitations, lightheadedness, dyspnea, fatigue) due to the arrhythmia. Medical therapy often fails to render a satisfactory response for the latter, prompting the search for alternative therapies. Surgical and, in the last 15 years, catheter ablation techniques have been devised to try to prevent episodes from starting. Groundbreaking work by Haïssaguerre¹ showed that premature discharges or rapid repeated firing from the pulmonary veins (PVs) could trigger AF episodes and that electrical isolation of the PVs could potentially cure the patient of AF. PV isolation currently is a painstaking process consisting of delivering radiofrequency energy in the left atrium to isolate these veins. Such procedures take 3-5 hrs. to complete depending on the complexity of the individual case, and a majority of patients require a 2nd or even 3rd procedure to achieve acceptable antiarrhythmic results. Despite considerable investigative effort, the exact pathophysiology of how PV triggers initiate and or maintain episodes of AF has been elusive.

Recently, Narayan et al² have developed an algorithm that has been licensed for use with a novel mapping technology (RhythmView, Abbott (Topera, Inc.), Menlo Park, CA) for analyzing atrial recordings during human AF, finding that >95% of cases demonstrate either a rapidly spinning rotor (small circuit) or very rapid focal impulse formation. Furthermore, they have shown that catheter ablation at these relatively circumscribed areas can significantly affect AF, either by substantial slowing of the rate or termination (to an atrial tachycardia or sinus rhythm). In the CONFIRM (CONventional vs Focal Impulse and Rotor Modulation) trial, patients were treated with either conventional mapping and ablation (largely PV isolation or PVI) vs ablation of rotors or sites of focal impulse formation as designated by the mapping algorithm, followed by conventional ablation (PVI). The authors found much higher acute and long-term efficacy when focal impulse and rotor modulation (FIRM procedure) was used (82.4 vs 44% freedom from AF at 24 months post procedure). Although CONFIRM was a controlled study, a randomized evaluation would be warranted.

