7.3 SECONDARY ENDPOINTS

Secondary endpoints are defined in Table 3 below. This study will also collect data relating to the health economics of the FIRM-guided procedure to conduct additional evaluations if primary endpoints are met.

Table 3 – Secondary Endpoints

Endpoint	Definition
Acute Effectiveness	
The acute success of FIRM-guided procedure is defined as elimination of the source of arrhythmias identified by FIRMap as indicated by;
 
 1. No evidence of the source on FIRMap immediately post-procedure, OR 2. Reduction of electrogram amplitude to <0.2mV in region designated by FIRMap

Table 4 – Additional Evaluations

Parameter	Definition
Total RF ablation time	Total RF ablation time as measured by total time of ablation lesion applications, from first ablation lesion to end of last lesion, will be documented. These values will be compared between the FIRM-guided and conventional ablation groups. If ablation for AT/atrial flutter is pursued, this ablation time will be documented separately
Repeat procedure and hospitalization	Any descriptive information regarding repeat procedures and re-hospitalizations will be compared between groups
Cumulative long-term freedom from AF	Cumulative long-term freedom from AF will be assessed at 12 months after the initial AF procedure but will permit results of repeat ablation
Cumulative long-term freedom from AF without use of anti-arrhythmic drugs	Cumulative long-term freedom from AF without use of anti-arrhythmic drugs will be assessed at 12 months after the initial AF procedure but will permit results of repeat ablation
Early Recurrence of AF/AT	Recurrences of sustained AF/AT in the first 3 months (blanking period).
Change in Atrial Function	Change in left atrial size and pulmonary vein inflow Doppler on echocardiogram (when available)
Change in Ventricular Function	Change in left ventricular ejection fraction and parameters of diastolic dysfunction (when available)
Quality of Life	Impact on quality of life, using patient-reported outcome instruments (EQ-5D and AFEQT), within treatment groups (change from pre-procedure to post-procedure follow-up timepoints) and between treatment groups. Analysis will be performed if primary endpoints are met.
Economic Analysis	Cost-effectiveness analysis based on clinical and patient-reported outcomes and resource utilization. Analysis will be performed if primary endpoints are met.

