3-D Electroanatomic Mapping	3-D electroanatomic maps may be created using CARTO (Biosense Webster, Johnson & Johnson) or Nav-X (St. Jude Medical) systems for documentation of anatomy and ablation lesion locations.
Induction of sustained AF	If the patient is not experiencing spontaneous, sustained AF (>5 min uninterrupted), induce sustained AF by atrial burst pacing, typically from the coronary sinus, with or without isoproterenol infusion in conventional clinical fashion. IF AF CANNOT BE SUSTAINED, THE PATIENT DOES NOT MEET THE INCLUSION CRITERIA FOR THE PROTOCOL AND THE PATIENT WILL UNDERGO CONVENTIONAL AF ABLATION PER PHYSICIAN DISCRETION.

Ablation data	For each ablation, the following data will be recorded: time, catheter size, lesion number, phrenic nerve assessment (if in an area of potential phrenic nerve proximity), approximate catheter tip location, duration of application, average temperature, and any comments.
FIRM-guided procedure	Under fluoroscopic guidance, a cardiac ablation catheter is passed to the location(s) identified as AF source rhythms (rotors or focal impulses). Therapy can be applied at up to 6 sites identified by the initial or repeated FIRMap per standard practice.
Conventional Ablation	Conventional ablation typically consists of isolation of all four pulmonary veins per guidelines. In addition, in the conventional arm of the study, data will be recorded regarding any additional ablation such as that performed per local routine for AF (e.g. CFAE, roof line, additional trigger elimination, etc.). Such additional ablation is NOT typically performed in the FIRM-guided limb where only PVI is typically performed for the purposes of AF ablation beyond FIRM-guided locations.
Additional ablation for other arrhythmias (non-AF)	Additional ablation for other arrhythmias will be noted for atrial tachycardia (AT) and/or right cavo-tricuspid isthmus ablation in the event that the patient has documented AT/atrial flutter prior to or during the procedure.
Electrograms	Electrogram recordings evaluating conduction into or out of each treated vein.

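### The acute-success denominator includes FIRM-arm subjects in whom no source was found, and the success rule does not say that every identified source must be gone

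*Protocol*

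**What the plan says.** Protocol section 16.2 B (repeated in the synopsis and in section 7.3, Table 3) introduces the endpoint with "The acute success of FIRM-guided procedure is defined as elimination of the source of arrhythmias identified by FIRMap as indicated by". Two alternatives follow: "No evidence of the source on FIRMap immediately post-procedure, OR" "Reduction of electrogram amplitude to <0.2mV in region designated by FIRMap". The result is a proportion of subjects, n/N, with "N = the total count of subjects for that arm in the ITT group". The two arms are then compared by a chi-square test of p_E against p_C.

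Four other places bear on this:

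- Section 16.1 defines ITT by randomization, meeting the eligibility criteria, and insertion of a mapping and/or ablation catheter. A source found on FIRMap is not a condition.
- Section 10.2, Table 6 expects several sources in one subject. The operator is to "determine which locations have focal or rotor rhythms that could be sources of the AF", and "Therapy can be applied at up to 6 sites identified by the initial or repeated FIRMap per standard practice".
- Section 4 reports earlier work "finding that >95% of cases demonstrate either a rapidly spinning rotor (small circuit) or very rapid focal impulse formation", so a small share had neither.
- Section 6.2 assigns the control arm to ablation without the FIRM-guided diagnostic step.

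**The concern.** An elimination rate should be counted among subjects who had something to eliminate. Here the stated denominator also takes in FIRM-arm subjects with no identified source. Each must be scored, and neither score is informative. As a success, the subject credits the procedure with an effect it did not have; as a failure, the subject charges it with missing a target that was absent. The protocol does not say which score applies.

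The unit is also loose. The procedure may address several sites per subject, but the criteria name one source and one region. The second criterion is an alternative to the first, so a single region below the amplitude limit could be taken as success while another identified source persists.

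Acute effectiveness is the only endpoint in Table 3, and it is the direct measure of the section 4.2 hypothesis that FIRM-guided procedures eliminate the source. A rate that shifts with an unstated scoring choice is weak evidence for that hypothesis.

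**Working it through.** The protocol states no acute success rate, and the alpha for this endpoint and the power section (16.4) are blacked out, so there is no figure to reproduce. The steps below size the issue.

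**1. Arm size.** Section 6.1 gives up to 350 subjects, 1:1, so 350 / 2 = 175 per arm at most.

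**2. Subjects with no source.** Section 4 gives more than 95% with a source, so the share without one, f, is at most about 0.05. That is 0.05 × 175 = 8.75, or about 9 subjects. With f = 0.025 it is 4.4, and with f = 0 it is none.

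**3. Effect on the rate.** Let r be the success rate among subjects with a source (assumed). Then:

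- no-source scored as failure: (1 − f) × r
- no-source scored as success: (1 − f) × r + f
- no-source left out of N: r

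With f = 0.05:

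| r | scored failure | scored success | left out |
|---|---|---|---|
| 0.80 | 76.0% | 81.0% | 80.0% |
| 0.90 | 85.5% | 90.5% | 90.0% |

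The two scorings differ by f, that is 5 points. Against the rate among subjects with a source, scoring success adds f × (1 − r), which is 1.0 or 0.5 points. Scoring failure removes f × r, which is 4.0 or 4.5 points.

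**4. Several sources.** Suppose a subject has k sources, each eliminated independently with probability q (k, q and independence are all assumed). Then P(all gone) = q^k and P(at least one gone) = 1 − (1 − q)^k.

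| q | k = 2: all / at least one | k = 3 | k = 6 |
|---|---|---|---|
| 0.80 | 64% / 96% | 51% / 99% | 26% / 99.99% |
| 0.90 | 81% / 99% | 73% / 99.9% | 53% / nearly 100% |
| 0.95 | 90% / 99.75% | 86% / 99.99% | 73.5% / nearly 100% |

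The gap runs from about 10 points (q = 0.95, k = 2) to about 74 points (q = 0.80, k = 6). These are illustrations. Six is the treatment limit, not an expected count. Outcomes within one heart under one operator are probably positively correlated, which narrows the gap; under complete dependence both readings give q and the gap is zero.

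**The case against.** The strongest reply is that the wording is generic. The objectives in section 5 and the hypothesis in 4.2 also speak of the source in the singular, while Table 6 plainly expects several locations, so the term reads naturally as collective. The first criterion is then a negative finding on the whole map: a FIRMap that still shows a rotor after the procedure hardly satisfies it. This largely stands.

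A reader might infer that the protocol scores one silenced region out of several as a success, or that sources found late or beyond the sixth are ignored. The documents do not support either as the stated rule. The first needs the second criterion read at its narrowest. Against the second, any source visible on the post-procedure map can count against success under the first criterion. Nor do the documents support treating the widest gap above as an expected effect, since it rests on assumed rates, independence and the treatment limit.

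The lead-in also ties success to a source identified by FIRMap, so a no-source subject could as naturally be a failure. That is fair, and it shows that the score is not fixed. It does not remove the subject from N.

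The synopsis refers to the statistical analysis plan for details, and rules for multiple sources could be set there. But the protocol itself states the criteria, n, N and the test. A detail left to another document differs from a denominator already written down.

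Finally, ITT does not take in everyone randomized: by Table 6, subjects whose AF cannot be sustained do not meet the inclusion criteria and so fall outside it. That narrows N, but it does not make it conditional on a source.

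**Conclusion.** The point holds for the denominator. Section 16.2 B includes FIRM-arm subjects with no identified source, and the first criterion can be met for them without any treatment effect. The consequence is at most about 5 points, or about 9 of 175 subjects, provided that the background figure carries over to this trial and the arm reaches full size.

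For several sources per subject, the finding is an ambiguity and not an error. The text allows success with identified sources remaining but does not require it, and the effect cannot be sized without assumed elimination rates, source counts and dependence.

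Correcting N also exposes the comparison. Controls are assigned no FIRM-guided diagnosis, so p_C has no source to score, and the chi-square test cannot stay once N is confined to subjects with a source.

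The endpoint is secondary. The primary effectiveness and safety analyses do not depend on it.

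**What to change.** Amend the definition consistently in the synopsis, Table 3 and section 16.2 B, and the denominator and analysis in 16.2 B:

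- Set N to FIRM-arm ITT subjects with at least one source identified by FIRMap. List no-source subjects separately.
- Define subject-level success as every source identified on the initial or a repeat FIRMap meeting the first or second criterion at the end of the procedure. A source that was not treated but is absent on the final map then counts as eliminated, in line with the first criterion.
- Report the FIRM-arm proportion with a confidence interval in place of the test of p_E against p_C.
- Add a sensitivity analysis over all FIRM-arm ITT subjects, counting no-source subjects as failures.
- Optionally, report the proportion of sources eliminated, with an interval that allows for clustering within subject.

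The cost is small but is more than wording. The reported acute success rate is likely to be lower than under a looser reading. The per-ablation data listed in Table 6 include no source identifier, electrogram amplitude or outcome per source, so a per-source outcome field may have to be added to the case report form; the optional per-source proportion depends on it.
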